5.9 Treatment Beyond Progression

Immunotherapeutic agents such as pembrolizumab may produce antitumor effects by potentiating endogenous cancer-specific immune responses. The response patterns seen with such an approach may extend beyond the typical time course of responses seen with cytotoxic agents and can manifest as a clinical response after an initial increase in tumor burden or even the appearance of new lesions. The date of initial progression will be used for the determination of the primary endpoint of overall response rate.

If radiologic imaging shows progressive disease (PD) and the patient is clinically stable, tumor assessment may be repeated by the site \geq 4 weeks later in order to confirm PD with the option of continuing treatment per below while awaiting radiologic confirmation of progression. If repeat imaging shows a reduction in the tumor burden compared to the initial scan demonstrating PD (i.e., PD is not confirmed), treatment may be continued as per treatment calendar. If repeat imaging confirms PD, patients will be discontinued from study therapy. In determining whether or not the tumor burden has increased or decreased, investigators should consider all target lesions as well as non-target lesions as defined in Section 11.1.5.1 and Section 11.1.5.2. The decision to continue study treatment after the first evidence of disease progression determined by radiologic imaging is based on the clinical status of the patient as described in the table below.

Patients may receive study treatment while waiting for confirmation of PD if they are clinically stable as defined by the following criteria:

- Absence of signs and symptoms (including worsening of laboratory values) indicating disease progression
- No decline in ECOG performance status
- Absence of rapid progression of disease
- Absence of progressive tumor at critical anatomical sites (e.g., cord compression) requiring urgent alternative medical intervention.

	Clinically Stable		Clinically Unstable	
	Imaging	Treatment	Imaging	Treatment
First radiologic evidence of PD	Repeat imaging at \geq 4 weeks to confirm PD	Continue study treatment while awaiting confirmatory scan	Repeat imaging at \geq 4 weeks to confirm PD per physician discretion only	Discontinue treatment
Repeat scan confirms PD	No additional imaging required	Discontinue treatment	No additional imaging required	Discontinue treatment
Repeat scan shows SD, PR, or CR	Continue regularly scheduled imaging assessments	Continue study treatment	No additional imaging required	Discontinue treatment

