5.7 Criteria for Removal from Study

Patients will be removed from study treatment when any of the applicable criteria, including confirmed progressive disease as the overall objective status (Section 11.1.5.3), adverse events, patient withdrawal or inability to follow study protocol as listed in Section 5.5. The reason for study removal and the date the patient was removed must be documented in the Case Report Form.

If radiologic imaging shows progressive disease (PD), tumor assessment should be repeated by the site \geq 4 weeks later in order to confirm PD with the option of continuing treatment while awaiting radiologic confirmation of progression as per section 5.9.

As per section 5.6 patients will be followed for 12 months after removal from study treatment or until death, whichever occurs first. Patients will be followed every three months by a telephone call or letter to assess vital status. Patients removed from study for unacceptable adverse event(s) will be followed longer if needed until resolution or stabilization of the adverse event.

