11.1.5 Response Criteria

11.1.5.1 Evaluation of Target Lesions

Complete Response (CR): Disappearance of all target lesions. Any pathological lymph nodes (whether target or non-target) must have reduction in short axis to <10 mm (<1 cm).

Partial Response (PR): At least a 30% decrease in the sum of the diameters of target lesions, taking as reference the baseline sum diameters.

Progressive Disease (PD): At least a 20% increase in the sum of the diameters of target lesions, taking as reference the smallest sum on study (this includes the baseline sum if that is the smallest on study). In addition to the relative increase of 20%, the sum must also demonstrate an absolute increase of at least 5 mm (0.5 cm). (Note: the appearance of one or more new lesions is also considered progressions).

Due to the natural evolution of MPM, an isolated new pleural or pericardial effusion should be only considered as a new lesion and thus calling for PD in case it is substantial, cytological malignancy is confirmed and the patient had not had any pleural or pericardial effusion history before treatment. However, any isolated new or significant increases in existing pleural or pericardial effusions in a stable or responding patient, without any other evidence of progression, is insufficient evidence to call progression.

Stable Disease (SD): Neither sufficient shrinkage to qualify for PR nor sufficient increase to qualify for PD, taking as reference the smallest sum diameters while on study.

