11.1.5.3 Evaluation of Overall Objective Status

The overall objective status for an evaluation is determined by combining the patient's status on target lesions, non-target lesions, new lesions, and previous objective status as defined in the following tables:

For Patients with Measurable Disease

Target Lesions	Non-Target Lesions	New Lesions	Previous Overall Objective Status –Preliminary PD	Overall Objective Status
CR	CR	No	N/A	CR
CR	Non-CR/ Non-PD Not Evaluated	No	N/A	PR
PR	Non-CR/ Non-PD/ Not evaluated	No	N/A	PR
SD	Non-CR/ Non-PD/ Not evaluated	No	N/A	SD
PD	Any	Yes or No	No	Preliminary PD
PD	Any	Yes or No	Yes	PD (Confirmed)
Any	Unequivocal PD	Yes or No	No	Preliminary PD
Any	Unequivocal PD	Yes or No	Yes	PD (Confirmed)
Any	Any	Yes	No	Preliminary PD
Any	Any	Yes	Yes	PD (Confirmed)
Not All Evaluated	CR Non-CR/ Non-PD Not evaluated	No	N/A	Not Evaluated (NE)

For Patients with Non-Measurable Disease

Non-Target Lesions	New Lesions	Previous Overall Objective Status –	Overall Objective Status
--------------------	-------------	-------------------------------------	--------------------------

		Preliminary PD	
CR	No	N/A	CR
Non-CR/Non-PD	No	N/A	Non-CR/ Non-PD
Not all evaluated	No	N/A	Not evaluated
Unequivocal PD	Yes or No	No	Preliminary PD
Unequivocal PD	Yes or No	Yes	PD (Confirmed)
Any	Yes	No	Preliminary PD
Any	Yes	Yes	PD (Confirmed)

Preliminary Progressive Disease (PD)

All of the following must be true:

- a. Progressive Disease defined in Section 11.5.1 and 11.5.2 in the target lesions and non-target lesions, or appearance of new lesions.
- b. No substantial clinical decline.

Confirmed Progressive Disease (PD)

Patients without substantial clinical decline who meet all the following would have confirmed PD as their overall object status:

- a. Previously considered Preliminary PD.
- b. Repeating imaging at least 4 weeks apart after initial imaging shows progressive disease.

Confirmed complete response (CR) or partial response (PR)

A subsequent scan must be obtained at least 4 weeks (within 8 weeks but not less than 4 weeks apart) following initial documentation of an objective status of either complete response (CR), partial response (PR), or preliminary progression (PD) for confirmation.

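### For a clinically stable patient, the Section 5.9 text and Section 11.1.5.3 can classify the same repeat scan in opposite ways: treatment may continue under the first, while Section 5.7 requires removal under the second

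*Combined protocol and SAP*

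**What the plan says.** Four places in the protocol bear on the repeat scan after a first PD scan.

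- **Section 5.9, text.** "If repeat imaging shows a reduction in the tumor burden compared to the initial scan demonstrating PD (i.e., PD is not confirmed", then "treatment may be continued as per treatment calendar". The comparator is the first PD scan, and no minimum reduction is given. The text adds that, in judging whether burden has risen or fallen, "investigators should consider all target lesions as well as non-target lesions as defined in Section 11.1.5.1 and Section 11.1.5.2". It also says that a patient whose repeat imaging confirms PD is discontinued, and it points to the table for the decision to continue.
- **Section 5.9, table.** For clinically stable patients, treatment stops if the repeat scan confirms PD. It continues in the row headed "Repeat scan shows SD, PR, or CR". Clinically unstable patients stop treatment in every row.
- **Sections 11.1.5.1 and 11.1.5.3.** Target-lesion PD is "At least a 20% increase in the sum of the diameters of target lesions, taking as reference the smallest sum on study", with an absolute rise of at least 5 mm. Stable disease is measured from the same smallest sum. PD is confirmed in a patient with earlier preliminary PD when this holds: "Repeating imaging at least 4 weeks apart after initial imaging shows progressive disease". Shrinkage from the first PD scan is not an exception.
- **Section 5.7.** Patients come off study treatment on listed criteria, "including confirmed progressive disease as the overall objective status", with a reference to Section 11.1.5.3.

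Section 5.5 lists disease progression as a reason to stop and refers to both Sections 5.7 and 5.9, without saying which prevails.

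**The concern.** The Section 5.9 sentence and Section 11.1.5.3 both decide whether PD is confirmed, but they compare the repeat scan with different things. One compares it with the first PD scan, the other with nadir. A tumour that grew well past the PD threshold and then shrank a little satisfies both rules at once: it is reduced from the first PD scan and still progressive against nadir.

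Two sites following the protocol in good faith could then handle the same patient differently. One would record PD as not confirmed and continue treatment. The other would record confirmed PD and stop. Time on treatment after first progression, and the recorded confirmed-PD status, would depend on which section was read. Extra cycles could also add adverse events to the between-group comparison of related grade 3 or higher events in Section 13.5.4.

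**Working it through.** The plan gives no figure to reproduce, so the check compares the rules.

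**Notation.** N is the smallest sum on study, I the sum at the first PD scan, and R the sum at the repeat scan at least 4 weeks later.

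**Rules.**
- Section 5.9 text: PD is not confirmed if R < I.
- Sections 11.1.5.1 and 11.1.5.3: after preliminary PD, PD is confirmed if R ≥ 1.2 × N and R − N ≥ 5 mm, that is, if R ≥ max(1.2N, N + 5).
- They disagree when max(1.2N, N + 5) ≤ R < I.

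**One patient.** N = 100 mm, I = 140 mm, R = 135 mm.
- First PD scan: 140/100 = +40% and +40 mm, so preliminary PD.
- Against I: 135 − 140 = −5 mm, and 5/140 = 3.6%. This is a reduction, so under the Section 5.9 text PD is not confirmed and treatment may continue.
- Against N: +35% and +35 mm. This is PD after preliminary PD, so Section 11.1.5.3 gives confirmed PD and Section 5.7 gives removal.
- Section 5.9 table: stable disease is also judged "taking as reference the smallest sum on study" in substance, so 135 mm is not SD, PR or CR. The row for confirmed PD applies and treatment stops.

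**Width of the band.**

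| N (mm) | I (mm) | max(1.2N, N + 5) | Repeat sums on which the rules disagree |
|---|---|---|---|
| 100 | 140 | max(120, 105) = 120 | 120 to just under 140 |
| 50 | 65 | max(60, 55) = 60 | 60 to just under 65 |
| 20 | 30 | max(24, 25) = 25 | 25 to just under 30 |
| 100 | 120 | max(120, 105) = 120 | none |

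**Where the rules agree.** With N = 100 and I = 140, R = 119 is PD under neither rule, and R = 140 is confirmed PD under both. If the first PD scan only just meets the threshold (last row), any reduction takes the sum below it, so no band exists.

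**New lesions.** The status table in Section 11.1.5.3 gives confirmed PD for a new lesion after preliminary PD, whatever the target lesions show. Section 5.9 anticipates a response after new lesions appear, but its sentence on burden names only target and non-target lesions. Section 11.1.5.2 speaks of the appearance of new lesions. The text does not settle whether a lesion that was new at the first PD scan, and has since shrunk but persists, counts again as new. This is an ambiguity, separate from the demonstrated conflict on target sums.

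**The case against.** The strongest reply is that only one sentence is out of line. Section 5.9 refers the continuation decision to its table, and the table agrees with Sections 11.1.5.3 and 5.7 once SD and PD are read as Section 11.1.5.1 defines them. The sentence is permissive, whereas Section 5.7 is mandatory. Section 5.9 also refers to Sections 11.1.5.1 and 11.1.5.2 and requires discontinuation once PD is confirmed. A careful reader could let the rest govern.

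Much of this stands. The table is not a further competing rule, and a reader who inferred three different definitions would be wrong. But the conflict remains. The sentence does more than permit: it classifies the scan as not confirming PD, which Section 11.1.5.3 contradicts. The cross-reference says which lesions to consider and does not change the comparator. Nothing says that the table overrides the text.

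Four stronger inferences are tempting and are not supported:

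- **That PFS or the primary response rate is biased.** Sections 11.1.7 and 13.5.3 count PFS to the first objectively documented progression, and Section 5.9 assigns the date of initial progression to the primary endpoint.
- **That the handling differs by arm.** Section 11.1.8 leaves response review to the local investigator and the regimens visibly differ, but the same text governs both arms. Differential use is a possibility, not a finding.
- **That every patient in the band is affected.** Clinically unstable patients stop whatever the repeat scan shows.
- **That a persisting new lesion shows the same contradiction.** The documents leave its classification open.

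**Conclusion.** The point holds as an internal contradiction in a stated rule. For a clinically stable patient whose repeat sum is below the first PD scan but still at least 20% and 5 mm above nadir, the Section 5.9 sentence says PD is not confirmed and permits treatment. Sections 11.1.5.1, 11.1.5.3 and 5.7 together classify PD as confirmed and require removal. The sentence also disagrees with its own table.

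The size depends on how far the first PD scan exceeds the threshold: a band of 20 mm for nadir 100 and first PD 140, and none when the threshold is only just met. These sums are illustrative, and the documents do not allow an estimate of how many patients fall in such a band. The consequence is variation in treatment duration and recorded confirmed-PD status, and possibly in adverse-event rates through exposure, which is not quantified. The contradiction is worth correcting because it bears on when treatment stops and costs little to remove.

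**What to change.** Reconcile the Section 5.9 sentence with the Section 5.9 table, Section 5.7 and Section 11.1.5.3, so that one definition of confirmed PD and one reference scan apply throughout. State explicitly the status and treatment consequence of a repeat scan that is smaller than the first PD scan but still PD against nadir. State also how a new lesion that has shrunk but persists is entered in the Section 11.1.5.3 table. The sponsor chooses the criterion; no view is taken here on which is right.

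The cost is a wording amendment. If the nadir reference is kept, the main change is to one sentence in Section 5.9. If the first-PD-scan reference is kept, the table, Section 11.1.5.3 and the reference in Section 5.7 need matching edits. Neither needs new scans, data or patients.

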6. DOSING DELAYS/DOSE MODIFICATIONS

6.1 PRO-CTCAE Data

PRO-CTCAE data should not be used for determining dose delays or dose modifications or any other protocol directed action.

6.2 Dose Modifications for Anetumab Ravtansine

Dose Level	Anetumab Ravtansine Dose
1	6.5 mg/kg
-1	5.5 mg/kg
-2	4.5 mg/kg

Neutrophil count decreased ^{1, 2}	Management/Next Dose
\leq Grade 1	No change in dose
Grade 2	No change in dose
Grade 3	Hold ² until $<$ Grade 2. Resume at one dose level lower.
Grade 4	Hold ² until $<$ Grade 2. Resume at one dose level lower.
1.	Patients with febrile neutropenia should hold ^{**} until $<$ grade 2 and resume at one dose level lower.
2.	G-CSF and other hematopoietic growth factors may be used during the study in the management of acute toxicity such as febrile neutropenia when clinically indicated per ASCO Recommendations for Therapeutic Use of CSF (63) or at the discretion of the investigator; however they may not be substituted for a required dose reduction.
3.	Patients requiring a delay of $>$ 12 weeks should go off protocol therapy.

Platelet count decreased¹	Management/Next Dose
≤ Grade 1	No change in dose
Grade 2	No change in dose
Grade 3	Hold ² until < Grade 2. Resume at one dose level lower.
Grade 4	Hold ² until < Grade 2. Resume at one dose level lower.
1.	Patients with active bleeding related to drug-induced thrombocytopenia should reduce by one dose level.
2.	Patients requiring a delay of > 12 weeks should go off protocol therapy.

Non-hematologic toxicities	Management/Next Dose
≤ Grade 1	No change in dose.
Grade 2	No change in dose.
Grade 3	Hold ¹ until ≤ Grade 2. Resume at same level or at one dose level lower, per investigator's discretion. ²
Grade 4	Off protocol therapy
1.	Patients requiring a delay of > 12 weeks should go off protocol therapy.
2.	Patients requiring > two dose reductions should go off protocol therapy.

Corneal Epitheliopathy	Definition	Management/Next Dose^{1, 2}
Grade 0	No pathologic changes	No change in anetumab ravtansine; ocular lubricants at discretion of investigator or ophthalmologist
Grade 1	Any stage of superficial punctate keratitis (SPK; as per the Oxford Schema for grading SPK from stage 0 to IV)	No change in anetumab ravtansine; ocular lubricants; add topical steroids if SPK shows treatment emergent progression by ≥ 2 SPK grades
Grade 2	Epithelial opacities; micro-cysts, micro-deposits; corneal erosion; non-central stromal opacity	Keep treatment dose level and schedule if the ophthalmological exam can be performed as needed; otherwise consider dose reduction by -1 dose level without dose schedule change at the discretion of investigator and ophthalmologist; intensive treatment with ocular lubricants enhanced with ointments; topical steroids; therapeutic contact lens may be considered at the discretion of investigator and ophthalmologist

Corneal Epitheliopathy	Definition	Management/Next Dose ^{1,2}
Grade 3	Corneal ulcer without risk of acute rupture; Central stromal opacity	1) Decrease dose to -1 dose level (or -2 dose level if event does not resolve to Grade ≤ 2 at the -1 dose level within 3 weeks) 2) Re-start at the original dose level if the first Grade 3 event resolves to Grade ≤ 2 within 3 weeks and does not recur 3) If not resolved within 3 weeks continue at reduced -1 dose level (or -2 dose level); Intensive therapy with ointments; topical steroids; therapeutic contact lens or occlusion recommended at the discretion of investigator and ophthalmologist
Grade 4	Corneal ulcer more severe than grade 3	Discontinue anetumab ravidansine; Intensive therapy with lubricants, ointments, topical steroids and antibiotics as needed; occlusion or therapeutic contact lens recommended; amniotic membrane transplant and other locally approved therapies to be considered at the discretion of investigator and ophthalmologist

 1. Other remedial therapies for corneal epitheliopathy may be added or substituted at investigator's discretion or according to the institutional standards. 2. Treatment decisions are based on corneal morphology changes only, not on visual acuity changes. 		

Recommended Measures in case of Eye Dryness and Ocular Hypertension
 
Changes in tear production as evaluated by the Schirmer test and in intraocular pressure (IOP) are not expected to occur as a direct consequence of anetumab ravidansine therapy. However, IOP may increase in some patients as a consequence of the therapy with topical steroid eye drops. Since these drugs may be required to manage the corneal epitheliopathy syndrome, IOP will be monitored during this study for patients receiving topical steroid eye drops.
 
Changes in IOP should be managed by an ophthalmologist. The remedial therapy should be chosen at investigator's discretion or according to the institutional standards; therapeutic measures can include modification of the type or posology of topical steroid eye drop, initiation of topical IOP lowering drugs and any other therapeutic options according to the local standard of care. Ophthalmological monitoring should be maintained until the IOP has returned to normal values.
		

Corneal Epitheliopathy	Definition	Management/Next Dose ^{1,2}
		
Reductions in tear production evaluated by the Schirmer test, while not being a part of the corneal epitheliopathy syndrome, are a risk factor for developing ocular surface disease including corneal epithelial defects. Therefore, the tear production will be evaluated in this study to determine if changes in this parameter may be helpful to identify patients at higher risk of developing the corneal epitheliopathy syndrome. Abnormal values in the Schirmer test should be evaluated and managed by an ophthalmologist to provide adequate protection to the corneal epithelium. The remedial therapy for the treatment-emergent changes in the Schirmer's test (dry eye) should be chosen at investigator's discretion or according to the institutional standards. These measures may include topical lubricants such as eye drops and ointments, punctual occlusion, use of therapeutic contact lenses and any other treatment approaches according to the local standard of care.

Note: PRO-CTCAE data should not be used for determining dose delays or dose modifications.

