- a: Physical exam at pre-study includes height/weight, vital signs, demographics and medical history. Physical exam at all other visits includes weight and vital signs. Vital signs include pulse, blood pressure and temperature.
- b: For all patients at screening then only those randomized to receive anetumab ravidansine: Perform ophthalmologic exam within 28 days prior to Cycle 1 Day 1. The exam will include visual acuity [BCVA according to ETDRS, or Snellen, or Landolt C or other charts], intra-ocular pressure, dry eye test [Schirmer test] and slit lamp. For all subsequent cycles after Cycle 1, visual acuity and a slit lamp examination will be repeated before infusion in every cycle and at safety follow-up visit, or more frequently at investigator's and ophthalmologist's discretion. The IOP measurement is to be repeated during anetumab ravidansine therapy if the

patient receives steroid eye drops for more than 10 days as treatment for corneal epitheliopathy. This measurement is performed at 2 weeks and 6 weeks after the initiation of steroid treatment. If IOP increases by < 7 mmHg, the frequency of IOP evaluation can be reduced to every 4 months. If IOP increases by ≥ 7 mmHg, a medical management plan with follow-up IOP evaluations will be initiated after consultation with an ophthalmologist and investigator. The Schirmer test is performed at baseline and then at C3D1 and C5D1. All these tests may be repeated during treatment at the investigator's discretion.

Note: Ophthalmologic exams do not need to be continued for patients assigned to combination therapy who later discontinue anetumab ravidansine due to non-ocular toxicities.

- c: Labs include albumin, alkaline phosphatase, total bilirubin, bicarbonate, BUN, calcium, chloride, creatinine, glucose, LDH, phosphorus, potassium, total protein, SGOT [AST], SGPT [ALT], sodium.
- d: Patients receiving pembrolizumab should be monitored for changes in thyroid function at the timepoints listed in the calendar and as clinically indicated for clinical signs and symptoms of thyroid disorders.
- e: Serum pregnancy test for females of childbearing potential.
- f: Echocardiogram or Multigated Acquisition Scan (MUGA; radionuclide angiography) is performed at pre-study and then only as clinically indicated.

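### Section 6.2 and study calendar footnote b give different instructions on when eye pressure is monitored in patients on steroid eye drops, and on when that monitoring ends

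*Combined protocol and SAP*

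**What the plan says.** **Section 6.2**, under the heading "Recommended Measures in case of Eye Dryness and Ocular Hypertension", makes two separate statements. The first concerns who is monitored: "IOP will be monitored during this study for patients receiving topical steroid eye drops". It gives no minimum course and no schedule. The second comes in the next paragraph, on managing a changed IOP: "Ophthalmological monitoring should be maintained until the IOP has returned to normal values".

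**Study calendar (Section 10), footnote b** lists IOP as part of the screening eye exam. The exam repeated each cycle after Cycle 1 consists of visual acuity and slit lamp, without IOP. Repeat IOP has its own rule. It is limited to the time on anetumab, and the condition it sets is: "patient receives steroid eye drops for more than 10 days as treatment for corneal epitheliopathy". On timing: "This measurement is performed at 2 weeks and 6 weeks after the initiation of steroid treatment". For smaller rises: "If IOP increases by < 7 mmHg, the frequency of IOP evaluation can be reduced to every 4 months". A rise of 7 mmHg or more leads to a management plan that includes further IOP checks, made in consultation with an ophthalmologist. The footnote also lets the investigator repeat any of the tests during treatment.

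The Note closing footnote b reads: "Ophthalmologic exams do not need to be continued for patients assigned to combination therapy who later discontinue anetumab ravidansine due to non-ocular toxicities".

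**Related text.** The corneal table in Section 6.2 includes topical steroids at Grade 1 (if the keratitis progresses) and at Grades 2 to 4. At Grade 4 anetumab is also discontinued. Section 6.4 allows one agent to continue when the other is stopped for a toxicity clearly attributable to it. Section 5.5 allows up to 12 months of anetumab and up to 24 months of pembrolizumab.

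**The concern.** Section 6.2 itself recognises that steroid drops given for corneal epitheliopathy can raise IOP, and that is why it asks for monitoring. A site that schedules visits from the calendar would apply a narrower rule than one working from Section 6.2. Neither place refers to the other or says which prevails.

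Two things are at stake. A rise during a short course, or during steroid treatment given after anetumab has stopped, may never be looked for. And a known, unresolved change may cease to be followed when anetumab stops for an unrelated toxicity. Both situations arise only in patients given anetumab.

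**Working it through.** There is no figure to reproduce, so the check applies both rules to the same patient, case by case.

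| Case | Section 6.2 | Footnote b | Result |
|---|---|---|---|
| 1. Drops for 10 days or less, anetumab continuing | IOP monitored | No repeat IOP scheduled; repeat is discretionary | Differ on trigger |
| 2. Drops for more than 10 days, rise of 7 mmHg or more, anetumab continuing | Monitor until normal | Management plan with further IOP checks | No gap |
| 3. Drops for more than 10 days, rise below 7 mmHg, anetumab continuing | Monitor until normal | Interval may widen to 4 months | Compatible: this sets a frequency, not an end |
| 4. IOP still changed when anetumab stops for a non-ocular toxicity | Monitor until normal | Note: eye exams need not continue | Opposite instructions |
| 5. Grade 4 corneal event: anetumab discontinued, topical steroids among the listed treatments | IOP monitored | Repeat IOP applies only during anetumab therapy; the Note does not apply, since the toxicity is ocular | Only Section 6.2 covers it |
| 6. IOP still changed when anetumab reaches its 12-month limit | Monitor until normal | Repeat IOP applies only during anetumab therapy; the Note does not apply | Only Section 6.2 covers it |

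**Does the Note reach IOP?** Footnote b names IOP as one component of the ophthalmologic exam, so a Note releasing patients from such exams can be read to include it. The footnote does not say whether a management plan already started for a rise of 7 mmHg or more continues once the Note applies.

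**Is case 4 an on-study situation?** Yes. Under Section 6.4 the patient may continue pembrolizumab after stopping anetumab for a toxicity clearly attributable to it.

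**Does another section close the gap?** Not clearly. Section 5.6 extends follow-up to resolution or stabilisation for patients removed from study because of unacceptable adverse events. It does not describe a patient who stops one agent and stays on the other. The routine exams each cycle do not help in case 1, because they do not include IOP.

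**How many patients?** The adverse event list in Section 7.1.1 puts corneal disorder in the category above 20%. Applied to 49 Group 2 patients, 20% is 0.20 × 49 = 9.8, so about 10 or more may have a corneal disorder. The documents do not give the share who receive steroid drops, the share whose courses last 10 days or less, or the share who stop anetumab with IOP still changed. The chain stops there.

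**The case against.** The best defence is that Section 6.2 states the principle and footnote b supplies the operating detail. Section 6.2 gives no timing; footnote b gives a trigger, two time points and a rule for each size of rise. The until-normal sentence says should rather than will, and it sits under a heading of recommended measures. The Note is permissive and can be read as limited to the exams scheduled in the calendar. Discretionary repeats are available, and footnote b does not say whether the 10 days are counted per course or in total.

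Part of this stands. It may explain the 10-day trigger, and it disposes of cases 2 and 3. It does not explain case 4, where one place says to continue and the other says there is no need, or case 5, where steroids are called for just as the footnote's window closes. The discretionary repeats are optional and limited to the treatment period.

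Several stronger readings are tempting and are not supported:

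- A reader might infer that Section 6.2 requires every patient on drops to be followed until IOP is normal. It does not. The until-normal sentence concerns patients whose IOP has changed.
- A reader might take the Note to cover any non-ocular reason for stopping anetumab. It names non-ocular toxicities only.
- A reader might count 5 to 10 affected patients by assuming that half to all of the 10 above receive drops. That share has no source in the documents, and the count would include patients on long courses who continue anetumab, whom both places cover.
- A reader might infer that the adverse event tables will understate harm in the combination arm. Adverse events are evaluated throughout and Section 7.4 requires all to be reported. After screening, scheduled eye exams apply only to patients on anetumab, so eye findings are sought more actively in that arm.

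**Conclusion.** The two places conflict and should be reconciled. They differ on the trigger (any topical steroid drops, against more than 10 days), on the period (during the study, against during anetumab therapy) and, for patients who stop anetumab for a non-ocular toxicity, on when monitoring ends.

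This rests on two readings: that footnote b's rule is the complete list of required repeat IOP measurements, and that the exams in the Note include IOP. The text supports both but states neither outright.

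It does not follow that a raised IOP will go unfollowed. Section 6.2 remains in force, so follow-up is lost only if a site applies the calendar over it, or if a rise outside the footnote's window is never measured. The number affected is unknown and could be small. The primary endpoint, sample size, futility rule and error rates are unaffected. This is a correction to the consistency of the safety instructions.

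**What to change.** Reconcile Section 6.2 and study calendar footnote b so that both state:

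- the same trigger for IOP monitoring in patients on topical steroid drops and, if a minimum course is kept, whether it is counted per course or in total;
- the same monitoring period and end, covering steroids given after anetumab has been discontinued;
- whether the Note applies to a patient with an unresolved IOP change, and whether a management plan already started continues.

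The clinical team decides the rule; none is proposed here. A cross-reference in each place to the other would help keep them aligned. The cost is a wording change and, depending on the rule chosen, a few extra IOP readings in affected patients.
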